**(3) Patient's impression (Patient Global Impression of Change [PGIC])**

The patient's impression about the condition at Week 13, as compared to the condition before the start of treatment (including the first day of treatment), will be rated on a 7-grade scale, ranging from 1 (markedly improved) to 7 (markedly worsened). In cases where treatment has been completed or discontinued before Week 13, the data at the time of completion (discontinuation) of treatment will be entered.

1. Markedly improved	2. Improved	3. Slightly improved	4. Unchanged
5. Slightly worsened	6. Worsened	7. Markedly worsened	

**(4) Physician's impression (Clinical Global Impression of Change [CGIC])**

The physician's impression about the condition at Week 13, as compared to the condition before the start of treatment (including the first day of treatment), will be rated on a 7-grade scale, ranging from 1 (markedly improved) to 7 (markedly worsened). In cases where treatment has been completed or discontinued before Week 13, the data at the time of completion (discontinuation) of treatment will be entered.

1. Markedly improved	2. Improved	3. Slightly improved	4. Unchanged
5. Slightly worsened	6. Worsened	7. Markedly worsened	

## 6.6 Patient summary

The appropriateness of continuation of treatment with the product will be checked on the day of safety evaluation. In cases where continuation of treatment with the product is not possible, one major reason should be selected from the alternatives given below. If adverse events, abnormalities in laboratory parameters or the death of patient is selected as a major reason, the relevant data should be entered in the "adverse event" field.

- [1] Insufficient clinical efficacy
- [2] Recovery (effective)
- [3] Adverse events
- [4] Abnormalities in laboratory parameters
- [5] Death of patient
- [6] Lost to follow-up
- [7] Others

In cases where no revisit has been made after the start of treatment, it should be entered in the "Confirmation of revisit after the start of treatment" field.

## 6.7 Efficacy evaluation

The efficacy of the product at Week 13 as compared to the condition before the start of treatment (including the first day of treatment) will be evaluated in the following way, and the judgment will be entered. In cases where treatment has been completed or discontinued before Week 13, the data at the time of completion (discontinuation) of treatment will be entered.

- [1] Date of efficacy evaluation
- [2] Clinical efficacy
  - Effective
  - Ineffective
  - Impossible to judge (enter the reason)

### Items of evaluation

The reason for judging "effective" or "ineffective" should be entered (multiple choices allowed).

- Changes in clinical symptoms
- Others

## 6.8 Adverse events

For evaluation of safety, the incidence of adverse events following the start of treatment with the product will be checked, and the following information will be entered. If any adverse event occurs, the investigator should take appropriate measures and immediately report it to the sponsor. When the causal relationship between the event and the product cannot be ruled out, observe the course of event or its sequela until they disappear or become stabilized at the level acceptable for the investigator and the sponsor.

A detailed investigation will be separately carried out if patients have intrauterine exposure or develop serious adverse reactions, adverse reactions not listed in the package insert and the like and the sponsor deems it necessary.

- [1] Day of safety evaluation (as a rule, day of last visit within 29 days after the start of treatment)
- [2] Presence/absence of adverse events
- [3] Name of adverse event
- [4] Date of onset
- [5] Measures taken

- [6] Seriousness
- [7] Outcome
- [8] Causal relationship to the product

[The following information should be entered if the adverse event is associated with abnormal changes in test data such as laboratory tests.]

- [1] Name of test
- [2] Reference value at the facility
- [3] Unit
- [4] Date of measurement
- [5] Results

Supplementary note: Adverse events mean all events unfavorable for the patient, arising after the start of treatment with the product, regardless of presence/absence of causal relationship to the product (including clinically significant abnormal changes in laboratory parameters). Serious adverse events mean death, life-threatening events, and events possibly causing hospitalization, extension of hospital stay period, permanent or marked disorders/disabilities, congenital anomalies/defects or other medically significant events/disorders.

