##### 5.3 Patient registration

After the user ID and password are issued to each investigator, the investigator will enter the following basic information on the patient registration screen: name initials of the patient (as needed), ID code, gender, birth date, starting date for treatment with the product and eligibility to the survey. Considering that the incidence of adverse events (peripheral edema, dizziness, etc.) was highest during the early stage of treatment with the product in phase 3 studies conducted in Japan, registration of patients should be done within 7 days after the start of treatment with the product, as a rule (within 14 days at latest) to enable appropriate collection of information on these adverse events.

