## 5.4 Observation period

The observation period will start on the first day of treatment with the product (Day 1) and last until Week 13 (Day 91). However, in cases where treatment has been completed or discontinued before Week 13, observation will be continued until completion (discontinuation) of treatment, and follow-up will be made for one week (7 days) after completion (discontinuation) of treatment. During this survey, safety will be evaluated on the day of the first visit after the end of the observation period (including the last day of the observation period), as a rule. In cases where treatment has been completed or discontinued, safety will be evaluated until the day of the first visit following 7-day period after the completion (discontinuation) of treatment, and safety information will be collected for this period.

**Supplementary note:** Completion of treatment means cases where further treatment with the product is judged unnecessary because of achievement of the purpose of treatment set at the start of treatment (e.g., cure of target diseases).

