**(2) Clinical findings**

The following information will be entered about the clinical findings before the start of treatment (including the first day of treatment) and during the period from the start of treatment to the day of safety evaluation. In cases where treatment has been completed or discontinued before Week 13, the data at the time of completion (discontinuation) of treatment will be entered. If the investigator considers that the change in any of the clinical findings from the pre-treatment status is abnormal, it will be reported as an adverse event.

**(2)-1 Information before the start of treatment (including the first day of treatment) and during the period from the start of treatment to the day of safety evaluation**

[Presence/absence of peripheral edema or edema in general]\*, [Presence/absence of dizziness, somnolence, loss of consciousness, syncope and potential for accidental injury], [Presence/absence of ophthalmological abnormalities], [Presence/absence of suicidal ideation (including suicide attempt and suicide after start of treatment)], [Presence/absence of pathologic changes in appetite and activity]

**Supplementary note\***: In cases where peripheral edema or edema in general is found, adverse events of the cardiovascular and respiratory systems also need to be checked. If any clinically significant change from the pre-treatment condition is found, it should be entered in detail in the field for adverse events.

**(2)-2 Information in cases of completed (discontinued) treatment with the product (information on the day of safety evaluation following 7-day period after the day of discontinuation [including Day 7 of this period])**

[Presence/absence of withdrawal symptom/rebound phenomenon]

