2.1. Study design

Study population

○ *Indication: Neuropathic pain*

○ *Dosage and administration: The usual starting dose in adults is 150 mg/day of pregabalin orally administered in 2 divided doses, which may be gradually increased to 300 mg/day over one week or longer. The dose may be adjusted depending on age and symptoms as*

appropriate, provided the daily dose may not exceed 600 mg and Lyrica should be orally administered in 2 divided doses regardless of the daily dose.

○ *Study population: The survey covers the patients satisfying all of the following requirements:*

- *Patients not participating in any other survey or study of Lyrica*
- *Patients never having used Lyrica before the survey*

Observation period

The observation period will start on the first day of treatment with Lyrica (Day 1) and last until Week 13 (Day 91). However, in cases where treatment has been completed or discontinued before Week 13, observation will be continued until completion (discontinuation) of treatment, and follow-up will be made for one week (7 days) after completion (discontinuation) of treatment.

During this survey, safety will be evaluated on the day of the first visit after the end of the observation period (including the last day of the observation period), as a rule. In cases where treatment has been completed or discontinued, safety will be evaluated until the day of the first visit following 7-day period after the completion (discontinuation) of treatment, and safety information will be collected for this period.

Completion of treatment means cases where further treatment with Lyrica is judged unnecessary because of achievement of the purpose of treatment set at the start of treatment (e.g., cure of target diseases).

Planned survey period

Survey period: January 2011 to April 2017

Registration period: January 2011 to January 2017 (-91 days from the survey period)

Target sample size and rationale

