10.1. Appendix 1: Details of data extraction

A1.1 Data to be used for tabulation and analysis

Data collected after the safety evaluation date will not be used in tabulation and analysis specified in this plan. Data on efficacy endpoints (Section 6.2) will be used even if they are collected after the safety evaluation date.

A1.2 Definition of visit schedule

Visit schedule	Endpoint	Definition [acceptable window]
Start of treatment	Laboratory tests and body weight	From 30 days before the first dose (date of start of treatment) in the survey to the date of start of treatment (Day 1)
After 4 weeks	Laboratory tests and body weight	Day 29 [Day 2 to Day 60]
After 13 weeks	Laboratory tests and body weight	Day 92 [Day 61 to Day 137]

If multiple data are collected within the acceptable window, the data whose date of evaluation is closer to the definition will be used for tabulation and analysis. If the difference from the definition is the same, the newer data will be used.

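### Protocol 6.8 [1] places the day of safety evaluation within about the first month, against the Week 13 or post-stopping visit in Protocol 5.4 and SAP 2.1, and SAP A1.1 does not say which date is its data cut-off

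*Protocol*

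**What the plan says.** Protocol 6.8, item [1], describes the survey-form entry: "Day of safety evaluation (as a rule, day of last visit within 29 days after the start of treatment").

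Protocol 5.4 gives a different default. For patients still on treatment, "safety will be evaluated on the day of the first visit after the end of the observation period", and the period ends at Week 13 (Day 91). For patients who complete or stop earlier, 5.4 and SAP 2.1 share this rule: "safety will be evaluated until the day of the first visit following 7-day period after the completion (discontinuation) of treatment". SAP 2.1 repeats both parts of the 5.4 rule and nowhere mentions a 29-day limit.

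SAP Appendix 1, A1.1 turns the date into a cut-off: "Data collected after the safety evaluation date will not be used in tabulation and analysis specified in this plan". Efficacy endpoints are exempt. A1.1 does not say whether the date is the one recorded under Protocol 6.8 [1] or one derived from the SAP 2.1 rule.

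The same day also bounds data entry in the protocol: treatment records (6.2), concomitant drug and non-drug therapy (6.3), clinical findings (6.4(2)) and laboratory tests (6.4(4)) are all entered up to it.

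**The concern.** A patient treated to Week 13 cannot satisfy both rules. Each is qualified as a general rule, but the defaults are about two months apart, and no passage explains the difference.

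The date closes the period over which the primary safety item, the incidence of adverse reactions (Protocol 7.2.1), is counted. There are two ways in which 6.8 [1] could shorten that period:

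- **At analysis.** A programmer who takes the recorded field as the A1.1 cut-off would drop adverse reactions, weights and laboratory values collected later.
- **At collection.** A site that followed 6.8 [1] literally could have stopped entering the bounded items at about Week 4. Those data would then not exist, and no SAP wording could restore them.

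In either case, a reader of the incidence table could not tell what length of follow-up it covers. Early stoppers already share a denominator with Week 13 patients, so this would add to mixed follow-up rather than create it.

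**Working it through.** **Planning figures.** The plan's own numbers reproduce. For a reaction with 0.1% incidence in 3400 patients (Protocol 3), 1 − (1 − 0.001)^3400 = 0.967, against the stated 97%. For vision-related events, 3400 × 0.0670 = 227.8, against the stated 227 or more. Neither depends on the safety evaluation date.

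**Reading the limit.** With the first treatment day as Day 1, the 29-day limit is Day 29 or Day 30, depending on how it is counted. Both are carried through.

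**Patient treated to Week 13 (Day 91).**
- Limit at Day 29: 91 − 29 = 62 days lost; 62/91 = 68.1%.
- Limit at Day 30: 91 − 30 = 61 days lost; 61/91 = 67.0%.
- These are minimum losses, because the last visit inside the limit may fall earlier.

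**Week 13 weight and laboratory window.** SAP A1.2 gives "Day 92 [Day 61 to Day 137"], which is 137 − 61 + 1 = 77 days. None falls on or before Day 30, so nothing in the window would be usable.

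**Onset categories.** SAP 8.2.3.1 defines the first 4 weeks as Days 1 to 28, so the category from over 4 to 13 weeks is Days 29 to 91: 91 − 29 + 1 = 63 days. At most Day 29 (1 of 63), or Days 29 and 30 (2 of 63), would remain. The category beyond 13 weeks would be empty.

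**Where the rules can agree.** If a patient stops on Day d, the earliest visit meeting the 7-day rule is Day d + 7.
- d + 7 ≤ 29 gives d ≤ 22.
- d + 7 ≤ 30 gives d ≤ 23.

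Patients who stop later, and all who are treated to Week 13, fall under conflicting rules.

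**Which date the rest of the plan fits.**

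| Place | Content | Fits a limit at about Day 29? |
|---|---|---|
| Protocol 6.4(1) | Weight at Week 4, at Week 13 and by the safety evaluation day | No |
| Protocol 6.4(2)-2 | For stopped patients, "information on the day of safety evaluation following 7-day period after the day of discontinuation" | Only if stopped by about Day 22-23 |
| SAP 8.2.1 | Discontinuation timing up to and beyond 13 weeks | No |
| SAP 8.2.3.1 | Onset categories up to and beyond 13 weeks | No |
| SAP A1.2 | Week 13 window, Day 61 to 137 | No |

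These passages fit Protocol 5.4 and SAP 2.1. Protocol 6.8 [1] is the exception.

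**The case against.** The strongest reply is that this is one stray phrase with no demonstrated consequence. The SAP's only rule for when safety is evaluated is in 2.1, so the natural reading of A1.1 is that date. Both rules allow exceptions. What sites were actually told is in the separate data entry sample, which is not among the documents. No passage shows that any recorded date followed 6.8 [1].

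Most of this stands, and it is why the point is minor. It does not remove the point: 6.8 [1] is the text that describes the field sites complete, and A1.1 does not name the variable it uses.

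A reader might make three stronger inferences that the documents do not support.

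- **That about two-thirds of adverse reactions would be lost along with two-thirds of the days.** Protocol 5.3 says that in the Japanese phase 3 studies "the incidence of adverse events (peripheral edema, dizziness, etc.) was highest during the early stage of treatment with the product". Days lost are therefore not events lost in proportion. The plan gives no onset distribution from which to calculate the share.
- **That the withdrawal and rebound finding would be cut off too.** Protocol 6.4(2)-2 places that finding on the safety evaluation day itself, so it does not fall after the cut-off for a site following that text.
- **That naming the date in the SAP settles everything.** Because the day also bounds data entry, some values might never have been entered.

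**Conclusion.** Protocol 6.8 [1] is wrong as written, in that it contradicts Protocol 5.4 and SAP 2.1. SAP A1.1 leaves open which date governs. This is an internal inconsistency of minor weight. Confidence is high that the contradiction exists; it does not extend to any consequence.

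The size is conditional. Where a recorded date followed 6.8 [1] and served as the cut-off, a patient treated to Week 13 would lose at least 61-62 of 91 observation days and all 77 days of the Week 13 weight and laboratory window from the safety tabulations, and some data may never have been entered. The number of such patients is not in the documents and may be zero. The effect on the incidence of adverse reactions cannot be determined. It would also be wrong to infer that the sample-size rationale fails: the stated 97% and 227 are unaffected.

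**What to change.** 1. Reconcile Protocol 6.8 [1] with Protocol 5.4 and SAP 2.1 as a recorded clarification. The SAP revision history marks the survey as completed from version 6.0, so this documents the intent and does not change collection.
2. In SAP A1.1, name the date variable. State that a recorded date earlier than the SAP 2.1 rule allows is not used to discard collected safety data. For those patients, keep collected data at least to Day 91, or to 7 days after stopping, working from the treatment dates recorded under Protocol 6.2.
3. Before analysis, list patients on treatment at Week 13 whose recorded date is before Day 91, and stopped patients whose recorded date is less than 7 days after stopping. Show separately those lost to follow-up or with no later visit, since they may legitimately lack the 7-day visit.
4. Report the number of such patients and their actual length of safety follow-up beside the incidence. If the count is zero, say so.

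The cost is one protocol clarification, a short SAP addition, one listing and a little programming. No extra patients are needed. Data that were never entered cannot be recovered.

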## 6.9 Major investigation items

The following events should be evaluated as major investigation items in this survey.

- [1] Peripheral edema and edema-related events
 

Information will be collected about the presence/absence of events related to peripheral edema and the course of patients before and after the onset of events. The situations on development of these events will be analyzed by means of factor analysis, including analysis of the site affected, dose of the product, concomitant therapy, background variables, etc. The package insert gives precautions on congestive heart failure in patients presenting symptoms related to edema. In 30 overseas placebo-controlled studies, the incidence of hypertension and dyspnea was higher in the patients developing peripheral edema than in patients free of peripheral edema, although the incidence of the other events did not differ markedly between these two groups. In view of these facts, information on cardiac function and the incidence of adverse events of the respiratory system will be also collected.
- [2] Dizziness, somnolence, loss of consciousness, syncope and potential for accidental injury
 

Information will be collected about the presence/absence of events related to dizziness, somnolence, loss of consciousness, syncope and potential for accidental injury and the course of patient's condition before and after the onset of events. The situations on development of these events will be analyzed by factor analysis, including analysis of the dose of the product, concomitant therapy, background variables and so on.
- [3] Vision-related events
 

Information will be collected about the presence/absence of events related to the eyes and the course of patient's condition before and after the onset of events. The situations on development of the events will be analyzed by factor analysis, including analysis of the dose of the product, concomitant therapy, background variables and so on.

Patients developing adverse events included in the major investigation items will be

separately investigated in detail if the sponsor deems it necessary.

## 7 Analysis plan

### 7.1 Analysis set

As a rule, safety analysis set will include patients who satisfy the eligibility criteria and have been confirmed to have taken the product at least once. As a rule, efficacy analysis set will include patients who are evaluable for efficacy in accordance with the separately set analysis plan (i.e., patients in whom efficacy was considered to be appropriately evaluated).

### 7.2 Methods of analysis

#### 7.2.1 Safety analysis

In the safety analysis set, the status of onset of adverse reactions and incidence of adverse reactions (percentage of patients developing adverse events for which the causal relationship with the product cannot be ruled out) will be set as primary analysis items. The factors affecting the incidence of adverse reactions will be also analyzed, for example, the incidence of adverse events will be summarized for each of the factors including background variable.

#### 7.2.2 Efficacy analysis

In the efficacy analysis set, the response rate will be set as a primary analysis item. As needed, explorative analysis of factors affecting the efficacy will be also carried out.

### 7.3 Time of analysis

#### 7.3.1 Periodical safety report

Interim analysis will be conducted at intervals of 6 months during the first two years after approval of the product and once a year during the subsequent reexamination period.

#### 7.3.2 Submission of application for reexamination

Final analysis will be conducted upon completion of the reexamination period.

## 8 Publication of the results

Pfizer Japan Inc. will publish the results of one of the following surveys. As needed, the company will publish the results of survey at academic society meetings, in journals and so on for the purpose of supplying information for proper use of the product.

- The survey registered in [www.clinicaltrials.gov](http://www.clinicaltrials.gov) (ClinicalTrials.gov), regardless of the reason for registration
- Other survey judged to have yielded scientifically or medically significant results

The timing for publication of the survey results will be determined based on whether or not the product has been approved in any country at the completion of the survey on the product.

The results of the survey on the product already approved in a given country should be published within one year after fixation of the patient's data collected during the last visit.

Only the published papers which can be accessed via the widely accepted and searchable databases on papers will be cited.

2.0/ February 20, 2015/ PPD	
Status of survey: Ongoing
 
5.2. Efficacy analysis set
 
Patients with clinical evaluations data collected were additionally included in the efficacy analysis set.
 
6.1. Safety endpoints
 
Suicide-related events were added.
 
7. Handling of missing data
 
Modified to exclude efficacy evaluation from Appendix “Definition of visit schedule”. LOCF (Week 13 [LOCF]) assessment was added for pain score and sleep interference score.
 
8.2.3.1. Adverse reactions
 
Tabulation of suicide-related events was added.
 
8.2.3.4. Exploratory analysis (safety)
 
Tabulation of the number and percentage of patients with adverse reactions by target disease (i.e., diagnosis of neuropathic pain) was added.
 
8.2.4.2. Pain score 8.2.4.3. Sleep interference score
 
Modified to exclude from Appendix “Definition of visit schedule”.
 
8.2.4.7. Exploratory analysis (efficacy)
 
Analyses by target disease (i.e., diagnosis of neuropathic pain) were added for each assessment of efficacy other than clinical efficacy.
 
A1.1 Data to be used for tabulation and analysis
 
The scope of data to be used was specified.
 
A1.2 Definition of visit schedule
 
Addition of the definition of Visit 1 and modification associated with the addition Handling of multiple observation data collected within the same visit window was additionally specified.
 
A.2.1 Subgroup analysis
 
Reference population for calculation of risk ratio and risk difference as subgroup analyses of safety and efficacy was additionally specified.
 
Others
 
Description adjustment

Version/ Date/ Author(s)	Summary of Changes/Comments
3.0/ February 17, 2016 PPD [REDACTED]	
Status of survey: Ongoing
 
5. Analysis sets
 
Handling of patients unable to be resurveyed was changed.
 
6.1. Safety endpoints
 
Definitions of major investigation items were additionally specified.
 
Pancreas-related events, thyroidal function-related events, change in appetite and activity-related events, and withdrawal symptom and rebound phenomenon-related events were added as other safety endpoints. Definition of weight-related endpoint was additionally specified.
 
8.2.3.1. Adverse reactions
 
Tabulation of major investigation item of peripheral edema and edema-related events was added.
 
Tabulation of other safety endpoints was added.
 
Others
 
Description adjustment

Version/ Date/ Author(s)	Summary of Changes/Comments
4.0/ February 17, 2017/ PPD [REDACTED]	
Status of survey: Ongoing
 
6.1. Safety endpoints
 
Accident-related events and euphoric mood-related events were added as other safety endpoints. Evaluation of adverse events was added for suicide-related events. Laboratory parameters to be assessed as a population, and laboratory parameters to be assessed were added.
 
8.2.3.1. Adverse reactions
 
Tabulation of major investigation item of peripheral edema and edema-related events was added.
 
Tabulation categories were added in the tabulation of major investigation item of dizziness, somnolence, loss of consciousness, syncope, and potential accidental for injury. Tabulation of the relationship between dosage and administration and development of adverse reaction and the relationship between prior medications and development of adverse reactions was added.
 
8.2.3.3. Other endpoints
 
Body weight: Tabulation of adverse reactions by presence or absence of weight gain was added.
 
Laboratory parameters: Calculation of summary statistics was added.
 
8.2.3.4. Subgroup analysis
 
Calculation of summary statistics of laboratory parameters was added for patients whose target disease is painful diabetic neuropathy.
 
8.2.3.5. Exploratory analysis (safety)
 
The plan was reviewed taking into consideration the tabulation added in Section 8.2.3. after the preparation of the first version of SAP.
 
8.2.4.1. Clinical efficacy
 
Definition (equation) of response rate was added.
 
9. Listings
 
Listings were added.
 
A1.1 Data to be used for tabulation and analysis
 
Handling of efficacy-related data was additionally specified.
 
A1.2 Definition of visit schedule
 
Laboratory parameters were added to endpoints.
 
Others
 
Description adjustment

Version/ Date/ Author(s)	Summary of Changes/Comments

5.0/ July 28, 2017 PPD [REDACTED]
	
Status of survey: Ongoing
 
5.4. Subgroup
 
Inpatient/outpatient status at the initial prescription, past medical history and complications were added for subgroup analysis of efficacy. Definition of subgroups based on initial dose was added.
 
6.1. Safety endpoints
 
Handling of serious adverse reactions or adverse events was specified.
 
8.1.1. Analysis of continuous data
 
Method of analysis of covariance was added.
 
8.2.2. Patient demographics and treatment history
 
Tabulation of pain score (continuous data) was added as patient demographics. Tabulation of patient demographic to be performed in subgroups based on initial dose was added.
 
Tabulation of daily dose (continuous data) and final daily dose was added as information on administration of Lyrica.
 
8.2.3.1. Adverse reactions
 
Tabulation of patients with special background was added.
 
8.2.3.5. Exploratory analysis (safety)
 
Tabulation to be performed in subgroups based on initial dose was added.
 
8.2.4.2. Pain score
 
Tabulation of responders was added.
 
8.2.4.6. Subgroup analysis (efficacy)
 
Analysis based on analysis of covariance model was added.
 
8.2.4.7. Exploratory analysis (efficacy)
 
Tabulation to be performed in subgroups based on initial dose was added.
 
Listings
 
Listings (listings of initial dose and patient demographics, etc.) were added.
 
Others
 
Description adjustment

Version/ Date/ Author(s)	Summary of Changes/Comments
6.0/ December 26, 2017/ PPD [REDACTED]	
Status of survey: Survey completed
 
6.1. Safety endpoints Skin disorder-related events were added.
 
8.2.1. General description of patients Modified to conduct the safety analysis set only in the tabulation by timing in the summary of discontinuation and dropouts.
 
8.2.2. Patient demographics and treatment history Modified to use information on past medical history and complications in view of consistency, etc. among surveys for clinical findings related to major investigation items at the start of treatment as patient demographics (as the tabulation of patient demographics by subgroup based on initial dose). Definition of analgesics, etc. was added as concomitant medications at the start of treatment. Details of the method of tabulation of daily dose (continuous data) were added as the information on administration of Lyrica.
 
8.2.3.1. Adverse reactions Modified to review the definition of major investigation item of peripheral edema and edema-related events to be used for detailed investigation. Tabulation of skin disorder-related events was added. Taking accumulated number of patients into consideration, scope of tabulation by target disease (i.e., diagnosis of neuropathic pain) was added to evaluate the relationship between prior and concomitant medications and development of adverse reactions.
 
8.2.3.4. Subgroup analysis (safety) Added tabulation to be performed based on factors showing a significant difference by testing to evaluate the relationship between patient demographics, etc. and development of adverse reactions.
 
8.2.4.6. Subgroup analysis (efficacy) Time points were specified for the analysis based on analysis of covariance model.
 
8.2.4.7. Exploratory analysis (efficacy) Taking accumulated number of patients into consideration, scope of tabulation by target disease (i.e., diagnosis of neuropathic pain) was added.
 
Listings Listing of events of major investigation items was deleted (the European risk management plan should be referred to as necessary because events to be handled as major investigation items are defined as Safety Specification in the European risk management plan of Lyrica).
 
Others Description adjustment
 
[REDACTED]

Version/ Date/ Author(s)	Summary of Changes/Comments
7.0/ February 13, 2018/ PPD [REDACTED]	
Status of survey: Survey completed
 
8.2.1. General description of patients
 
Tabulation of disease name of patients excluded from efficacy analysis because of non-target disease of the survey was added.
 
8.2.3.1. Adverse reactions
 
Tabulation of major investigation item of dizziness, somnolence, loss of consciousness, syncope, and potential for accidental injury by factor was added.
 
For patients with special background, pediatric patients were additionally specified and tabulation of serious adverse reactions was added.
 
8.2.3.4. Subgroup analysis (safety)
 
Added tabulation to be performed based on factors showing a significant difference by testing to evaluate the relationship between patient demographics, etc. and development of adverse reactions.
 
8.2.4.6. Subgroup analysis (efficacy)
 
Added tabulation to be performed based on factors showing a significant difference by testing to evaluate the relationship between patient demographics, etc. and efficacy.
 
Others
 
Description adjustment

8.0/ March 9, 2018 PPD [REDACTED]	
Status of survey: Survey completed
 
8.2.3.4. Subgroup analysis (safety)
 
Added tabulation to be performed based on factors showing a significant difference by testing to evaluate the relationship between patient demographics, etc. and development of adverse reactions.

2. Introduction

This statistical analysis plan describes a plan of statistical analysis to be performed in the drug use investigation of Lyrica® Capsule (hereinafter referred to as Lyrica). In this plan, sentences cited from the protocol are shown in *italic*.

